The enrollment is defined as the patient's entry into the study; which is the point at which informed consent form is signed. Data will be collected on a minimum of 40 eligible pediatric patients who signed informed consent. These patients should be aged ≥ 10 to <18 years at enrollment, are diagnosed with non-transfusion dependent thalassemia and require to be treated with deferasirox or started deferasirox treatment 12 months or less prior to enrollment. These patients will be followed for up to 5 years from the start of deferasirox treatment. Retrospective data collection will be done for patients whom have started deferasirox 12 months or less prior to enrollment.

The baseline is defined as the timeframe before the patient starts treatment with deferasirox.

In patients who have protocol specified assessments performed prior to the date of first deferasirox treatment, the baseline data will be collected if it is within the following timeframe prior to the date of starting deferasirox treatment (see also table 7-2):

- 1.5 months for all laboratory assessments
- 6 months for vital signs, weight, height, LIC, ECG, ECHO, CMR, ocular and audiometry assessments
- 12 months for pubertal assessments (Tanner stage).

Post baseline data will be collected from the start date of deferasirox and then on for five years.

Investigational treatment

Deferasirox dispersible tablets

Deferasirox dispersible tablet is currently marketed in three dosing strengths (125, 250, 500 mg) and is dosed based on body weight. The currently approved dose range is up to 40 mg/kg/day.

Deferasirox dispersible tablets prescribed by physicians in actual practice setting will be used in accordance with the local label.

Initial deferasirox dose 10 mg/kg/d, 7 d/wk in accordance with the deferasirox prescribing information. Dose titration of deferasirox may be performed based on LIC levels as measured by magnetic resonance imaging (MRI) and/or SF levels and safety markers in steps of 5–10 mg/kg/d as defined by local label requirements.

Deferasirox Film Coated Tablets (FCTs)

Because of the chronic nature of chelation therapy and the importance of patient compliance, an improved deferasirox formulation for oral administration has been developed.

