7.7.1.2 Safety Set

The Safety Set includes all patients who received at least one dose of deferasirox during the study and have at least one post-baseline safety assessment. For post-baseline safety assessments, if a patient has any assessment taken a day after treatment start date for examination based assessments, e.g. laboratory, the patient will be included. For AE/ Death patients with an AE start date/ death date on or after the start date of treatment will be considered as having as least one post-baseline safety assessment and will be included in the safety set.

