7.7.5 Secondary objectives

To evaluate the incidence of serum creatinine and ALT increases in 7.7.5.1 actual practice setting

Counts and frequencies will be provided on Safety Set for patients with:

- Serum creatinine > 33 % above baseline and the age adjusted ULN (as per local normal ranges) in at least two consecutive post-baseline measurements at least 7 days apart from each other:
- SGPT (ALT) above 5 x ULN in at least two consecutive post-baseline measurements at least 7 days apart from each other.

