7.7.5.4 To evaluate sexual development by gender

Shift tables for Tanner stages to compare baseline to the last on-study value will be provided. Descriptive statistics will be also provided for age at assessment for each Tanner stage.

Number and percentages of patients who are below, within and above the Marshal standards (Marshall and Tanner 1970) (mean age \pm 2 SD) for each Tanner stages by gender will be provided.

The age of patients at time they reach the next Tanner stage will be flagged based on the Marshal standards and the listing will be provided.

Number and percentage of patients at different Tanner stages will be provided by gender and baseline age category (10 - < = 12, > 12 - < 18) at enrollment, at the end of each year and at end of study.

To evaluate long term efficacy of deferasirox as measured by serum 7.7.5.5 ferritin and LIC

The time-course of serum ferritin and LIC and its absolute/relative changes from baseline will be summarized on FAS using descriptive statistics quarterly.

Counts and frequencies will be provided on FAS for patients:

- achieving a SF <300 ng/mL at any time during study;
- achieving LIC <3 mg Fe/g dw at any time during study;
- restarting deferasirox treatment after temporary interruption due to one of the two criteria mentioned above (SF <300 ng/mL or LIC <3 mg Fe/g dw at any time during study).

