7.7.6.1 Analysis set and grouping for the analyses

The overall observation period will be divided into three mutually exclusive segments:

- pre-treatment period: from day of patient's informed consent to the day before first dose of study medication except for patients who started their study medication 12 months or less prior to enrollment. For these patients, the pre-treatment period will include any day before the first dose of study medication.
- on-treatment period: from day of first dose of study medication to 30 days after last dose of study medication
- post-treatment period: starting at day 30+1 after last dose of study medication

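### A pre-dose assessment on the start day cannot be baseline and may count as on-treatment; the sections disagree on that day, and restart is reported over the FAS instead of over patients who stopped

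*Protocol*

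**What the plan says.** Section 7.1 states: "The baseline is defined as the timeframe before the patient starts treatment with deferasirox". It adds: "the baseline data will be collected if it is within the following timeframe prior to the date of starting deferasirox treatment". The windows are 1.5 months for laboratory tests, 6 months for vital signs, growth, LIC, cardiac, ocular and audiometry assessments, and 12 months for Tanner stage. Section 7.3 and the Abstract repeat the rule, and the Table 7-2 footnotes word their windows in the same way. For the other side of the line, 7.1 says: "Post baseline data will be collected from the start date of deferasirox and then on for five years".

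Three other sections also place the boundary:

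- 7.7.1.2, on Safety Set entry: "if a patient has any assessment taken a day after treatment start date for examination based assessments, e.g. laboratory, the patient will be included".
- 7.7.6.1: "on-treatment period: from day of first dose of study medication to 30 days after last dose of study medication".
- 7.7.5.2 starts the first post-baseline laboratory window after the first intake of drug.

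The creatinine and ALT increases in 7.7.5.1 are reported thus: "Counts and frequencies will be provided on Safety Set for patients with" the two criteria listed there. Safety Set membership requires a dose and a post-baseline safety assessment, but no baseline value. Section 7.7.5.5 gives, on the FAS, counts and frequencies of patients "restarting deferasirox treatment after temporary interruption due to one of the two criteria mentioned above".

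**The concern.** In routine care, blood may be drawn and height and weight measured at the visit where the drug is started, before the first dose. Such a value is a genuine pre-treatment measurement, yet the protocol does not accept it as baseline. The Amendment 4 rationale in Section 3 shows that this is a practical matter: sites had been entering start-date values as baseline. Section 7.1 also recommends duplicate creatinine and liver tests before treatment begins. A same-day pre-dose sample satisfies that recommendation and is still refused as baseline.

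The study imposes no visits, so a missing earlier value cannot be assumed to exist, and with a minimum of 40 patients each lost baseline matters. A pre-dose value placed on the treatment side could also make a shift table show a change under drug that was present before drug.

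**Working it through.** **Where a pre-dose sample on the start day falls**

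| Section | Rule | Status of the sample |
|---|---|---|
| 7.1, 7.3, Table 7-2 footnotes | Baseline precedes the start date | Not baseline |
| 7.1 | Post-baseline from the start date | Post-baseline |
| 7.7.6.1 | On-treatment from the first-dose day | On-treatment |
| 7.7.1.2 | Examinations count from the day after | Does not qualify for the Safety Set |
| 7.7.5.2 | First window opens after first intake | Outside the window |

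The opening definition in 7.1 could on its own admit a pre-dose sample, but the collection rule goes by date: "In patients who have protocol specified assessments performed prior to the date of first deferasirox treatment, the baseline data will be collected" only within the stated windows. No section makes an exception for the start day.

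**Which endpoints need a baseline**

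- Need one: change-from-baseline summaries; creatinine more than 33% above baseline (7.7.5.1); the Table 7-3 ranges for creatinine and for ALT/AST, the latter through the twice-baseline condition.
- Need none: the primary proportion with drug-related SAEs, ALT above 5 x ULN, SF below 300 ng/mL, LIC below 3 mg Fe/g dw.

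**The plan's own figures**

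Section 7.5 tabulates the chance of at least one AE among 40 patients, 1 - (1 - p)^40. For p = 3%, 4%, 5%, 6%, 10% and 15% this gives 0.704, 0.805, 0.871, 0.916, 0.985 and 0.998, which agree with the printed 0.70, 0.80, 0.87, 0.92, 0.99 and 1.00. None of these depends on the baseline rule.

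**Illustration for creatinine**

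Let f be the share of 40 Safety Set patients without a creatinine baseline. The documents give no f; 10%, 25% and 50% are assumptions, as are the true incidences of 5% and 10%. Evaluable n = 40(1 - f). If the unevaluable patients stayed in the denominator, the proportion would be p(1 - f). The chance of at least one case is 1 - (1 - p)^n.

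| f | n | True 5%: over 40 | P(at least 1) | True 10%: over 40 | P(at least 1) |
|---|---|---|---|---|---|
| 10% | 36 | 4.5% | 0.84 | 9% | 0.98 |
| 25% | 30 | 3.75% | 0.79 | 7.5% | 0.96 |
| 50% | 20 | 2.5% | 0.64 | 5% | 0.88 |

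Over evaluable patients the expected proportion stays at 5% or 10%. For a mean change with unchanged SD, the standard error rises by 1/sqrt(1 - f): 1/sqrt(0.9) = 1.05, 1/sqrt(0.75) = 1.15, 1/sqrt(0.5) = 1.41.

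**Restart**

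Table 6-1 describes this endpoint as reinitiation after a discontinuation under the stopping rule, so only patients who stopped can have the event. With invented counts of 8 stopped and 4 restarted among 40, the FAS gives 4/40 = 10%, while the patients at risk give 4/8 = 50%.

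**The case against.** A reader might infer that patients without a baseline are kept as non-cases and that the incidence endpoints are therefore diluted. The protocol does not say so. Section 7.7.5.1 names the population without saying how a patient lacking a baseline is classified. Missing-data detail is left to an SAP that is not shown and may restrict the denominator. Nor would dilution through the baseline rule reach the endpoints listed above as needing none. Change summaries lose patients; they are not diluted, and n is shown.

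Other points in the plan's favour also stand:

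- Start-date values are still collected, so they can be recovered.
- The wider windows for growth and Tanner stage, and the recommended pre-treatment tests, make a sole same-day value less likely.
- A single same-day creatinine cannot create a case by itself, because two values at least 7 days apart are needed.
- A misplaced value distorts a shift only in a patient who also has an earlier baseline.
- FCT patients are asked to dose before noon, so an untimed same-day sample may be post-dose.
- The restart count appears whatever the denominator.

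What the objection does not remove is the date-based exclusion and the conflicting cut-offs. An SAP that reclassified start-day values as baseline would contradict a rule the protocol states repeatedly. The FAS denominator for restart is likewise stated outright, not left open.

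**Conclusion.** The point holds for the treatment of the start day and for the restart denominator. As written, a pre-dose start-day assessment is refused as baseline, may enter the on-treatment side of the 7.7.6.3 shift tables, and does not count for Safety Set entry. The loss falls on change-from-baseline summaries, the creatinine criterion and the baseline-relative Table 7-3 ranges. Its size cannot be taken from the documents. The dilution, detection and standard-error figures are illustrations under assumed shares, and the dilution also assumes that unevaluable patients remain in the denominator. The restart example shows the direction of the error, not an expected result. The primary endpoint is not affected by the baseline rule. This should be corrected, chiefly because usable baselines are recovered cheaply in a study of about 40 patients.

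**What to change.** In 7.1, 7.3, 7.7 and the Table 7-2 footnotes (and the Abstract, which repeats the rule), define baseline for laboratory and examination data as values on or before the first-dose date within the existing windows. Take same-day values as pre-dose unless they are timed after the dose. Start post-baseline and on-treatment laboratory and examination values the day after first dose, which matches 7.7.1.2; AEs continue to count from the first-dose day.

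Report the creatinine proportion among patients with a baseline and at least two post-baseline values, next to the Safety Set count and the number not evaluable. In 7.7.5.5, report restart as a proportion of patients who stopped by the stopping rule. The SF and LIC endpoints should not be made conditional on a baseline at or above the limit; that would redefine them and exclude further patients.

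The cost is wording, an eCRF note and minor programming. The downside is that an occasional untimed same-day value taken after the dose will be treated as baseline.

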Non-interventional study (NIS)' in this context is used synonymously with 'observational study', i.e., does not involve any kind of intervention, experimental or otherwise. In these studies, interviews, questionnaires and blood samples may be performed as normal clinical practice.

6 Research question and objectives

This observational study will evaluate the long term safety of deferasirox therapy in pediatric patients ≥ 10 to ≤ 18 years at enrollment with NTDT in actual practice setting.

Table 6-1 Objectives and Endpoints

Objectives	Endpoints	Analysis
Primary		
Evaluate the long term safety of deferasirox	Proportion of patients having SAEs that are considered to be related to study drug up to 5 years from the start of deferasirox treatment	Section 7.7.4
Secondary		

Evaluate the incidence of serum creatinine and SGPT (ALT) increases in actual practice setting	The proportion of patients having (up to 5 years from the start of deferasirox treatment): Serum creatinine > 33 % above baseline and above the age adjusted ULN in at least two consecutive post-baseline measurements at least 7 days apart from each other. SGPT (ALT) above 5 x ULN in at least two consecutive post-baseline measurements at least 7 days apart from each other	Section 7.7.5.1
Evaluate renal and hepatic safety parameters over time	Absolute/relative changes from baseline of SGPT (ALT), SGOT (AST), total bilirubin, alkaline phosphatase, serum creatinine, creatinine clearance quarterly up to 5 years. Proportion of patients having hepatic and renal clinical events that are considered to be related to study drug up to 5 years from the start of deferasirox.	Section 7.7.5.2
Evaluate growth by gender	Absolute change in BMI, weight and height from baseline to EOS Proportion of patients falling behind in growth based on height, weight and BMI	Section 7.7.5.3
Evaluate sexual development by gender	Mean age at assessment for each Tanner stage Changes from baseline to the last on-study value of all Tanner stage parameters.	Section 7.7.5.4
Evaluate long term efficacy of deferasirox as measured by serum ferritin and LIC	Absolute/relative change in SF and LIC from baseline to EOS Proportion of patient achieving a SF <300 ng/mL Proportion of patients achieving LIC <3 mg Fe/g dw Proportion of patients reinitiating deferasirox after discontinuation due to a "stopping rule" *	Section 7.7.5.5

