It is expected that the stopping rule for treatment discontinuation will be followed by physicians and reintroduction of deferasirox therapy will take place if the LIC and/or SF levels increase above the thresholds as per local label requirements. (Stopping rule: In general it is recommended that treatment should be stopped once a satisfactory body iron level has been achieved (LIC <3 mg Fe/g dw or serum ferritin <300 ng/mL). In the context of this noninterventional trial where no therapy protocol is imposed and patients are treated based on investigator judgment following local practice, investigators are advised to follow the stopping rules described above)

It is recommended that serum creatinine be assessed in duplicate before initiating therapy. Serum creatinine, creatinine clearance (estimated with the Cockcroft-Gault or MDRD formula in adults and with the Schwartz formula in children) should be monitored weekly in the first month after initiation or modification of therapy with deferasirox, and monthly thereafter.

It is recommended that serum transaminases, bilirubin and alkaline phosphatase be checked before the initiation of treatment, every 2 weeks during the first month and monthly thereafter.

It is recommended that serum ferritin be monitored monthly in order to assess the patient's response to therapy and to avoid overchelation.

Treatment

Since the study is non-interventional, deferasirox treatment duration is at the discretion of the physician. The maximum duration of deferasirox treatment observed will be 5 years.

Patient numbering and screening

Each patient is identified in the study by a subject ID with a maximum length of 9 digits, which is a combination of his/her site ID (the first 4 digits of the subject ID) and subject number (the last 5 digits of the subject ID) when the patient is first enrolled. The site ID is assigned by Novartis to the investigative site. Upon signing the informed consent form, the patient is assigned the subject ID by the physician. At each site, the first patient is assigned subject number 1, and subsequent patients are assigned consecutive numbers (e.g. the second patient is assigned the subject number 2, the third patient is assigned the subject number 3). Once assigned, the subject number must not be reused for any other subject and the subject number for that individual must not be changed, even if the patient is re-screened.

Definition of End of Study

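### Raw growth and Tanner change in Table 6-1 start from a baseline up to 6 or 12 months before first dose, so they can include untreated growth or puberty

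*Protocol*

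**What the plan says.** Section 7.1 of the protocol, repeated in 7.3, treats baseline as a period and not a visit: "The baseline is defined as the timeframe before the patient starts treatment with deferasirox". Chart values are accepted back to a limit that depends on the measure. For growth it is "6 months for vital signs, weight, height, LIC, ECG, ECHO, CMR, ocular and audiometry assessments"; for puberty it is "12 months for pubertal assessments (Tanner stage". The footnotes to Table 7-2 repeat both limits. On the other side of first dose, "Post baseline data will be collected from the start date of deferasirox and then on for five years".

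Table 6-1 names these endpoints that start from that baseline:

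- Growth: "Absolute change in BMI, weight and height from baseline to EOS".
- Sexual development: "Changes from baseline to the last on-study value of all Tanner stage parameters".

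Section 7.7.5.3 adds the time course of raw change from baseline. Section 7.7.5.4 adds "Shift tables for Tanner stages to compare baseline to the last on-study value will be provided". None of these places adjusts for the time between the baseline reading and first dose.

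The same sections also plan summaries read against age: SDS at baseline, yearly and at end of study, with change; CDC percentile trajectories and category shifts; age at each Tanner stage; comparison with published pubertal standards; and plots by age at assessment beside the historical transfused cohort.

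**The concern.** Children aged 10 to under 18 grow and move through puberty whether treated or not. If the baseline reading is months older than the first dose, the raw difference to a later value contains growth that happened off drug. The feasibility text in 7.1 says the registry is meant to assess what deferasirox does to growth and development, and Table 7-2 marks height, weight and Tanner stage as safety assessments. A change that joins untreated and treated time answers that question less cleanly than it could.

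The amount also differs between patients, because it depends on how old each child's baseline reading happens to be. For adverse events, 7.7.6.1 and 7.7.6.2 separate pre-treatment from on-treatment time. Raw growth change and Tanner change have no equivalent separation.

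**Working it through.** The plan gives no figure on this point to reproduce, so the check is how far the change interval can exceed time on drug.

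**Inputs**
- Largest gap before first dose, g: 0.5 year for height and weight, 1.0 year for Tanner stage (7.1, 7.3, Table 7-2 footnotes).
- Years from first dose to the last measurement, T, taken here as time on drug (interruptions ignored). The upper end is 5 years: "The maximum duration of deferasirox treatment observed will be 5 years" (7.1). Smaller T arises at early points of the time course and in patients withdrawn early, since 7.3 requires withdrawal after permanent discontinuation other than under the stopping rule.
- Assumption: constant velocity over the interval.

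**Formulas**
- Excess of the change interval over time on drug = g / T.
- Pre-treatment share of the change interval = g / (g + T).

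| T (years) | Height/weight, g = 0.5: excess | share | Tanner, g = 1.0: excess | share |
|---|---|---|---|---|
| 5 | 10% | 9.1% | 20% | 16.7% |
| 3 | 16.7% | 14.3% | 33.3% | 25.0% |
| 2 | 25% | 20.0% | 50% | 33.3% |
| 1 | 50% | 33.3% | 100% | 50.0% |

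Example: a 5-year completer with a 6-month-old height has a change spanning 5.5 years, and 0.5/5.5 = 9.1% of it precedes treatment.

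**A less extreme gap.** If height and weight baselines were spread evenly over the window (an assumption), the average gap would be 0.25 year and the excess 5% at 5 years, 8.3% at 3, 12.5% at 2 and 25% at 1.

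**In centimetres.** The documents give no growth velocity. Assuming 3 to 9 cm/year, a 6-month-old height adds 1.5 to 4.5 cm of pre-dose growth, or 0.75 to 2.25 cm at the average gap. I do not convert the Tanner gap into stages, because the documents give no rate of progression.

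**What a slowing would look like.** Suppose growth slows by one third, on drug only. After one year, a child with a 6-month-old baseline shows 6 + 12 × 2/3 = 14 months' worth of growth, against 12 expected over the year on drug. The break-even slowing s solves 6 + 12(1 − s) = 12, so s = 50%. With a 3-month gap, 3 + 12(1 − s) = 12 gives 25%. For a 5-year completer with a 6-month gap, 6 + 60(1 − s) = 60 gives 10%. These sums matter only if raw change is judged against growth expected over time on drug.

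**Age-referenced summaries.** SDS and percentile categories are read at the age of measurement, so normal growth before first dose largely cancels; only a drift in SDS or percentile before treatment would carry over. Age at Tanner stage, the comparison with published standards and the historical plots use no change from baseline.

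**The case against.** The strongest reply is that the plan does not rely on raw change to see slow growth. Section 7.7.5.3 already has SDS change, CDC trajectories and percentile shifts. Table 6-1 has a second growth endpoint, the proportion falling behind, and names age at each Tanner stage. The comparison with the historical cohort is by age at assessment. This stands, and it limits the point to which summary carries the endpoint.

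A reader might infer that the plan credits untreated growth to deferasirox, so that a real slowing would be hidden. The documents do not support this. The protocol never labels change from baseline as change on drug, all analyses are descriptive, and no benchmark of expected raw growth over time on drug is planned. Nor is the distortion always flattering: weight or BMI can fall before treatment, and a child near final height or at the last Tanner stage has little or nothing to add.

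It is also fair that the windows are outer limits, and that the choice among several in-window values may be left to an SAP that is not shown. But choosing the latest pre-dose value does not help a child whose only value is old. With no imposed visit schedule, some such children are foreseeable. The windows and the Table 6-1 endpoints are themselves protocol content.

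**Conclusion.** The point holds in a limited form. Raw change in height, weight and BMI, and Tanner change and shifts, are named or planned outputs that can contain up to 6 or 12 months of untreated time with no correction. The worst case for a 5-year completer is modest: an interval 10% (height, weight) or 20% (Tanner) longer than time on drug. It reaches 50% or 100% only with the oldest permitted baseline and a single year on drug. These figures rest on the maximum window and constant velocity, which is a rough approximation at these ages; the actual gaps are unknown.

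It does not follow that the registry would miss a growth effect, since the age-referenced analyses largely escape the problem. The weakness is that the better protected measure, SDS change, sits only in 7.7.5.3, while Table 6-1 gives endpoint status to the unprotected raw change.

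**What to change.** - **Table 6-1:** name change in height, weight and BMI SDS as the growth endpoint, with each SDS computed at the actual measurement date. The analysis is already in 7.7.5.3.
- **7.7.5.3:** report raw height and weight change as cm/year and kg/year over the actual interval between the two measurements.
- **Both growth and Tanner:** summarise the gap between the baseline reading and first dose, so that readers can see how much it matters.
- **7.7.5.4:** keep the full Tanner shift table and add a sensitivity table limited to patients whose baseline is close to first dose, with the cut-off fixed in advance. Stage changes from older baselines should stay in the main table: dropping them would discard real progression on drug and lean towards apparent delay.

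The cost is a change of wording and a little programming; the planned age-at-assessment analyses already need the measurement dates. With a planned minimum of 40 patients, the sensitivity table will have small cells. The collection windows stay as they are, and no visits or data are added.
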